8.4 Laboratory Assessments

8.4.1 Variables

The following treatment-emergent laboratory abnormalities will be summarized. A treatment emergent laboratory abnormality is defined as any laboratory abnormality with an onset date on or after the date of the first dose of study drug.

Category	Abnormality	SDTM LBTESTCD	Grading System
Hematology	WBC decreased	WBC	CTCAE
	ANC decreased	NEUT	CTCAE
	Lymphocytes increased Lymphocytes decreased	LYM	CTCAE
	Platelets decreased	PLAT	CTCAE
	Hemoglobin increased Hemoglobin decreased	HGB	CTCAE
Serum chemistry	Albumin decreased	ALB	CTCAE
	ALP increased	ALP	CTCAE
	Amylase increased	AMYLASE	CTCAE
	ALT increased	ALT	CTCAE
	AST increased	AST	CTCAE
	Calcium, corr increased Calcium, corr decreased	CACORR	CTCAE
	Creatinine increased	CREAT	CTCAE
	GGT increased	GGT	CTCAE

Category	Abnormality	SDTM LBTESTCD	Grading System
	Glucose increased Glucose decreased	GLUC	CTCAE
	LDH increased	LDH	Sponsor
	Lipase increased	LIPASE	CTCAE
	Magnesium increased Magnesium decreased	MG	CTCAE
	Phosphate decrease	PHOS	CTCAE
	Potassium increased Potassium decreased	K	CTCAE
	Sodium increased Sodium decreased	NA	CTCAE
	Total bilirubin increased	BILI	CTCAE
	Uric acid increased ²	CYURIAC	CTCAE
Urine chemistry	UPCR increased	PROTCRT	Sponsor
Endocrinology ¹	Thyroid Stimulating Hormone increased Thyroid Stimulating Hormone decreased	TSH	HLN

¹ TSH is held in the SDTM "chemistry" laboratory category; will use HLN = high, low, normal classification based on normal range

² Uric acid increases will be graded only as Grade 1 or Grade 4. Grade 2 is not defined per CTCAE v4 and Grade 3 cannot be distinguished from Grade 1 based upon the result alone.

Sponsor-defined grades are to be applied to the following analytes:

LDH:

- Grade 1 if $>$ ULN to $\leq 2 \times$ ULN
- Grade 2 if $> 2 \times$ ULN to $\leq 3 \times$ ULN
- Grade 3 if $> 3 \times$ ULN

UPCR:

- Grade 1 if ≥ 17.0 to ≤ 121.0 mg/mmol (≥ 0.15 to ≤ 1.0 mg/mg)
- Grade 2 if > 121.0 to ≤ 396.0 mg/mmol (> 1.0 to < 3.5 mg/mg)
- Grade 3 if > 396.0 mg/mmol (> 3.5 mg/mg)

8.4.2 Analysis

All laboratory data parameters and visits will include flags for values above or below laboratory reference ranges. Toxicity grades will be assigned programmatically by applying the CTCAE v 5

guidelines. Only results with assessment dates through the end of the safety observation period (see Section 4.6) will be tabulated in summary tables.

Laboratory summaries will be presented in SI units. Continuous laboratory test results will be summarized by treatment group using descriptive statistics for actual values and for changes from baseline by scheduled visit. For test results which are below or above the quantification level, the imputed values as described in Appendix C will be used for deriving the grade and then summarized. Box-Whiskers plots may also be presented at each scheduled visit (with visits shown on x-axis) for some laboratory parameters for IDMC review purposes. Line graphs for mean change from baseline \pm standard deviation will also be presented at each scheduled visit (with visits shown on x-axis) for the following laboratory parameters.

- Renal function
 - Blood urea nitrogen (BUN)
 - Creatinine
- Liver function panel
 - Total bilirubin
 - ALT
 - AST

Tables summarizing baseline laboratory values and the incidence of laboratory abnormalities by baseline and maximum post-baseline CTCAE grade over all records will be presented. In addition, the following summaries will also be presented:

- A. Liver function abnormalities will be assessed as follows:
 - Shift from baseline based on normal ranges
 - Summaries of subjects meeting Hy's Law laboratory screening criteria as shown below:
 - $> 3 \times$ ULN (ALT or AST), $> 2 \times$ ULN Total Bilirubin, and $< 2 \times$ ULN ALP
 - $> 3 \times$ ULN (ALT or AST), $> 2 \times$ ULN Total Bilirubin, and $\geq 2 \times$ ULN ALP
 - $> 3 \times$ ULN (ALT or AST), $> 2 \times$ ULN Total Bilirubin
- B. For renal failure surveillance, a summary of subjects meeting renal failure laboratory screening criteria as shown below will be provided:
 - Serum creatinine $\geq 3.0 \times$ ULN and $\geq 2.0 \times$ baseline value or
 - Estimated Glomerular Filtration Rate (eGFR) $\leq 50\%$ of the baseline value or
 - eGFR < 30 mL/min/1.73 m² and $\geq 25\%$ reduction from the baseline value

$eGFR = 186 \times (\text{Creatinine in mmol per L} / 88.4)^{-1.154} \times (\text{Age})^{-0.203} \times (0.742 \text{ if female}) \times (1.210 \text{ if black})$ [from the UK CKD eGuide on the Renal Association website: <http://egfrcalc.renal.org/>]

C. Categorical summaries for baseline status for TSH and Free T4 will be presented. In addition, categorical summaries for post-baseline TSH and Free T4 status among subjects with TSH and Free T4 in the normal range at baseline will also be presented.

For descriptive summaries of change from baseline in continuous laboratory variables, only central lab results will be considered. For analyses of shift in grade from baseline or worst grade after baseline, all available results will be considered regardless of whether from the central or local lab.

Summary Type	Include central lab results?	Include local lab results?
Subject-Incidence of Treatment Emergent Laboratory Abnormalities in Selected Laboratory Tests by CTCAE Grade	Y	Y
Change from Baseline in Laboratory Values	Y	N
Shift from Baseline in Laboratory Values by CTCAE Grade	Y	Y
Worsening Shift of at Least 2 Grades from Baseline in Selected Laboratory Tests	Y	Y
Shift from Baseline in Laboratory Values by High/Low/Normal	Y	Y
Shift from Baseline in Laboratory Values by Sponsor-defined Grades	Y	Y
Laboratory Abnormalities with a subject-incidence of $\geq 5\%$ (All Grades) or $\geq 2\%$ (Grades 3-4) in either arm	Y	Y
Laboratory Abnormalities with a subject-incidence of $\geq 5\%$ (All Grades) or $\geq 2\%$ (Grades 3-4) in the experimental arm	Y	Y
Laboratory Abnormalities with an increase in subject-incidence of $\geq 5\%$ (All Grades) or $\geq 2\%$ (Grades 3-4) in the experimental arm	Y	Y

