- f. Alanine aminotransferase (ALT), AST, and alkaline phosphatase (ALP) $\leq 5 \times$ upper limit of normal (ULN).
- g. Total bilirubin $\leq 2 \text{ mg/dL}$ ($\leq 34.2 \mu\text{mol/L}$).
- h. Serum albumin $\geq 2.8 \text{ g/dL}$ ($\geq 28 \text{ g/L}$).
- i. Serum creatinine $\leq 1.5 \times$ ULN or calculated creatinine clearance $\geq 40 \text{ mL/min}$ ($\geq 0.67 \text{ mL/sec}$) using the Cockcroft-Gault equation (see [Table 3](#)).
- j. Urine protein/creatinine ratio (UPCR) $\leq 1 \text{ mg/mg}$ ($\leq 113.2 \text{ mg/mmol}$), or 24-h protein $\leq 1 \text{ g}$.

11. Capable of understanding and complying with the protocol requirements and must have signed the informed consent document prior to any screening assessment except those procedures performed as standard of care within the screening window.

12. Sexually active fertile subjects and their partners must agree to use highly effective methods of contraception that alone or in combination result in a failure rate of less than 1% per year when used consistently and correctly (see [Appendix H](#)) during the course of the study and for 5 months after the last dose of study treatment. A barrier method (eg, condom) is also required.

13. Female subjects of childbearing potential must not be pregnant at screening. Female subjects are considered to be of childbearing potential unless one of the following criteria is met: documented permanent sterilization (hysterectomy, bilateral salpingectomy, or bilateral oophorectomy) or documented postmenopausal status (defined as 12 months of amenorrhea in a woman > 45 years-of-age in the absence of other biological or physiological causes. In addition, females < 55 years-of-age must have a serum follicle stimulating hormone (FSH) level > 40 mIU/mL to confirm menopause). Note: Documentation may include review of medical records, medical examination, or medical history interview by study site staff.

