6.6.2.4. Management of Hepatobiliary Adverse Events

As this study will be evaluating subjects with advanced HCC, hepatobiliary AEs are expected to occur relatively frequently.

Elevations of aminotransferases and bilirubin have been observed during treatment with some anticancer therapies including cabozantinib, atezolizumab, and sorafenib. Modifications of study treatment may be appropriate to address these events, and management guidance for these agents in response to increases in aminotransferases and bilirubin is provided in this section.

General Guidance for Aminotransferase and Bilirubin Abnormalities

Patients with advanced liver cancer may have elevations of aminotransferases (ALT and AST) or bilirubin due to their disease. As such, subjects on this study may enroll with elevations of AST/ALT up to 5 \times ULN at baseline. It is recommended that subjects with elevations of ALT, AST, and/or bilirubin have more frequent laboratory monitoring of these parameters.

Evaluation of subjects with elevated transaminases or total bilirubin should be individualized and guided by the presence of specific risk factors such as illnesses which affect liver function (eg, infectious and non-infectious causes of hepatitis, liver cirrhosis, thrombosis of portal or hepatic vein), concomitant hepatotoxic medication, alcohol consumption, and cancer related causes. If possible, hepatotoxic concomitant medications should be discontinued in subjects who develop increased values of ALT, AST, or bilirubin. For patients with elevated LFTs, concurrent medication, viral hepatitis, and toxic or neoplastic etiologies should be considered and addressed, as appropriate.

Subjects with right upper-quadrant abdominal pain and/or unexplained nausea or vomiting should have liver function tests (LFTs) performed immediately and reviewed before administration of the next dose of study drug.

Guidance for Management of Hepatotoxicity

Guidance is provided on management of hepatotoxicity related to atezolizumab in [Table 28](#) and to cabozantinib in [Table 29](#).

Table 28: Management Guidelines for Hepatic Events Associated with Atezolizumab

Severity of Event	Management

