^c Resumption of atezolizumab may be considered in subjects who are deriving benefit and have fully recovered from the immune-related event. The decision to rechallenge subjects with atezolizumab should be based on the investigator's benefit-risk assessment and documented by the investigator. The Medical Monitor is available to advise as needed.

Table 29: Management Guidelines for Hepatic Events Associated with Cabozantinib

Severity of Event	Management
If ALT/AST is $\leq 3.0 \times$ ULN at baseline and increases to $\geq 5.0 \times$ ULN	
Interrupt cabozantinibMonitor LFTs more frequently until return to baseline valuesIf event resolves to baseline, or values stabilize at clinically acceptable levels, cabozantinib may be resumed at a reduced doseDiscontinue cabozantinib if hepatic dysfunction is not reversible despite temporary interruption of cabozantinib or drug-related ALT or AST $> 3 \times$ ULN in combination with total bilirubin $> 2 \times$ ULN without reasonable other explanation, consistent with DILI
If ALT/AST is $> 3.0 \times$ ULN to $\leq 5.0 \times$ ULN at baseline and doubles compared with the baseline values OR If ALT/AST is $> 3.0 \times$ ULN to $\leq 5.0 \times$ ULN at baseline and increases are less than double but are accompanied by progressive elevations of total bilirubin and/or elevations of coagulation tests (eg, INR).	
Interrupt cabozantinibMonitor LFTs more frequently until return to baseline values.If event resolves to baseline, or values stabilize at clinically acceptable levels, cabozantinib may be resumed at a reduced doseDiscontinue cabozantinib if hepatic dysfunction is not reversible despite temporary interruption of cabozantinib or drug-related ALT or AST $> 3 \times$ ULN in combination with total bilirubin $> 2 \times$ ULN without reasonable other explanation, consistent with DILI

ALT, alanine aminotransferase; AST, aspartate aminotransferase; DILI, drug-induced liver injury; INR, international normalized ratio; LFT, liver function test; ULN, upper limit of normal.

Hepatic Encephalopathy

Hepatic encephalopathy (HE) is a brain dysfunction caused by liver insufficiency. Hepatic encephalopathy is not uncommon in HCC patients and can be due to acute liver failure, portal systemic shunting and cirrhosis (Wong et al 2011, Willson et al 2013).

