8.3. Adverse Events of Special Interest

Adverse events of special interest (AESIs) consist of immune-mediated AEs associated with ICIs, cases of potential DILI, and suspected transmission of an infectious agent by the study treatment ([Table 31](#)).

AESIs will be reported to the Sponsor or designee using the SAE reporting form irrespective of whether the event is serious or nonserious; all AESIs must be reported within 24 hours using the SAE process as described in [Section 8.2](#).

Guidance for management of immune-mediated AEs associated is provided in [Section 6.6.2.2](#) and can also be found in the local prescribing information and Investigator's Brochure for atezolizumab.

Table 31: Adverse Events of Special Interest

Category	Event
DILI	
Cases of potential DILI that include an elevated ALT or AST in combination with either an elevated bilirubin or clinical jaundice, as defined by Hy's Law and based on the following observations:
Treatment-emergent ALT or AST $> 3 \times$ baseline value in combination with total bilirubin $> 2 \times$ ULN (of which $\geq 35\%$ is direct bilirubin)Treatment-emergent ALT or AST $> 3 \times$ baseline value in combination with clinical jaundice
Other	
Suspected transmission of an infectious agent by the study treatment, as defined below
Any organism, virus, or infectious particle (eg, prion protein transmitting transmissible spongiform encephalopathy), pathogenic or non-pathogenic, is considered an infectious agent. A transmission of an infectious agent may be suspected from clinical symptoms or laboratory findings that indicate an infection in a patient exposed to a medicinal product. This term applies only when a contamination of study treatment is suspected.
irAE	
Pneumonitis
irAE	
Colitis
irAE	
Endocrinopathies: diabetes mellitus, pancreatitis, adrenal insufficiency, hyperthyroidism, and hypophysitis
irAE	
Hepatitis, including AST or ALT $> 10 \times$ ULN
irAE	
Systemic lupus erythematosus
irAE	
Neurological disorders: Guillain-Barré syndrome, myasthenic syndrome or myasthenia gravis, meningoencephalitis, myelitis, and facial paresis

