8.3 Adverse Events of Special Interest

Adverse events of special interest (AESIs) consist of immune-mediated AEs associated with immune checkpoint inhibitor therapies, cases of potential drug induced liver injury (DILI) and suspected transmission of an infectious agent by the study treatment. Analysis of DILI is discussed in Section 8.4 and cases transmission of infectious agent by study treatment, if any, will be discussed in patient narratives.

Immune checkpoint inhibitor therapy is complicated by side effects known as immune-mediated adverse events classified as AESIs. The sponsor has defined a set of events to track these adverse events known to be associated with immune checkpoint inhibitors that have potentially serious consequences or were determined to warrant ongoing routine surveillance. Each AESI is a grouped clinical term comprising a set of pre-defined AE preferred terms for potentially immune-related events that are related pathophysiologically and provide a consistent, reproducible, and transparent compilation of safety information over time. The specific list of preferred terms employed for analyses will be provided in the clinical study report.

The following summaries will be provided for AESIs for the P-Safety and Safety Populations. These summaries will be for all AESIs during the extended safety observation period.

TEAE included	Row-levels (sorted by)	Columns
Subject Incidence by SOC, Preferred Term and Severity		
All AESIs	AESI and PT (AESI, PT within AESI by descending frequency)	Worst severity: All Grades, Grade 3-4, Grade 4, Grade 5
AESIs leading to discontinuation of any treatment component	AESI and PT (AESI, PT within AESI by descending frequency)	Worst severity: Grade ≥ 3 , Grade 3, Grade 4, Grade 5
AESIs leading to discontinuation of all treatment components	AESI and PT (AESI, PT within AESI by descending frequency)	Worst severity: Grade ≥ 3 , Grade 3, Grade 4, Grade 5
AESIs leading to discontinuation of IV treatment components	AESI and PT (AESI, PT within AESI by descending frequency)	Worst severity: Grade ≥ 3 , Grade 3, Grade 4, Grade 5
AESIs leading to dose delay/reduction of any treatment component	AESI and PT (AESI, PT within AESI by descending frequency)	Worst severity: Grade ≥ 3 , Grade 3, Grade 4, Grade 5
AESIs leading to dose delay/reduction of all study treatment components	AESI and PT (AESI, PT within AESI by descending frequency)	Worst severity: Grade ≥ 3 , Grade 3, Grade 4, Grade 5

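### The SAP counts potential drug-induced liver injury by multiples of ULN, the protocol defines it by multiples of baseline, and no planned table counts the protocol's event

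*SAP*

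**What the plan says.** Protocol 8.3 (Table 31) lists potential DILI among the AESIs and gives two routes to it. The first is treatment-emergent ALT or AST above three times the "baseline value in combination with total bilirubin" above 2 x ULN, at least 35% of it direct. The second is ALT or AST above three times the "baseline value in combination with clinical jaundice".

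SAP 8.3 repeats that potential DILI is an AESI and then says "Analysis of DILI is discussed in Section 8.4". SAP 8.4.2 has one summary that combines aminotransferases with bilirubin, headed as Hy's "Law laboratory screening criteria as shown below". Its three rows all require ALT or AST above 3 x ULN with total bilirubin above 2 x ULN. One adds ALP below 2 x ULN, one adds ALP at or above 2 x ULN, and one has no ALP condition. None has a baseline term, a direct-bilirubin fraction or a jaundice route.

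On entry values, Protocol 6.6.2.4 states that "subjects on this study may enroll with elevations of AST/ALT up to 5" x ULN. Protocol 4.2 caps total bilirubin at 2 mg/dL.

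The protocol also has a second wording. Table 29, on hepatic events associated with cabozantinib, describes drug-related ALT or AST above 3 x ULN with bilirubin above 2 x ULN "without reasonable other explanation, consistent with DILI".

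**The concern.** A reader of the study report will take the SAP 8.4.2 rows as the incidence of the protocol's DILI event, because SAP 8.3 points there and nowhere else. The AESI tables in SAP 8.3 are built from grouped preferred terms for potentially immune-related events, and DILI is expressly sent elsewhere. If the two definitions select different subjects, the by-arm DILI figure answers a different question from the one the protocol asks.

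This matters more here than in most trials. The disease affects the liver, abnormal aminotransferases are allowed at entry, and the protocol expects hepatobiliary events to be relatively frequent. A fixed ULN cut cannot separate an on-treatment aminotransferase rise from an elevation already present at randomization.

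**Working it through.** There is no planned figure to reproduce. The check compares the two thresholds directly.

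**Inputs.** The SAP ALT/AST cut is 3 x ULN (SAP 8.4.2). The Table 31 cut is 3 x baseline (Protocol 8.3). Entry ALT/AST is at most 5 x ULN (Protocol 4.2 and 6.6.2.4). Entry bilirubin is at most 2 mg/dL (Protocol 4.2). The bilirubin ULN is not in the documents; 1.0 to 1.3 mg/dL is assumed.

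**Step 1: the ALT/AST cut.** Write baseline as b x ULN. The SAP cut is 3 x ULN for every b. The Table 31 cut is 3b x ULN.

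| b | Table 31 cut (x ULN) | Peaks where only the SAP ALT/AST cut is met | Peaks where only the Table 31 ALT/AST cut is met |
|---|---|---|---|
| 0.5 | 1.5 | none | above 1.5, up to 3 |
| 0.8 | 2.4 | none | above 2.4, up to 3 |
| 1 | 3 | none | none |
| 2 | 6 | above 3, up to 6 | none |
| 3 | 9 | above 3, up to 9 | none |
| 4 | 12 | above 3, up to 12 | none |
| 5 | 15 | above 3, up to 15 | none |

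**Step 2: over-inclusion.** When b is above 3, an unchanged ALT or AST already meets the SAP enzyme condition. A subject at 4 x ULN throughout whose bilirubin reaches 2.1 x ULN is counted by the SAP. Table 31 would need ALT or AST above 3 x 4 = 12 x ULN. The missing direct-fraction condition widens the SAP count further.

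**Step 3: does bilirubin have to rise?** Twice the assumed ULN is 2.0 to 2.6 mg/dL. The entry cap of 2.0 mg/dL does not exceed any value in that range. A subject whose liver tests all stay at entry levels therefore cannot meet both conditions; bilirubin must rise on treatment.

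**Step 4: omission.** Take b = 0.6 with a rise to 2.5 x ULN. The fold-change is 2.5 / 0.6 = 4.2, above 3. If bilirubin exceeds 2 x ULN with at least 35% direct, this is a Table 31 case. The SAP does not count it, because 2.5 is below 3. When b is at or above 1, 3b is at least 3, so anyone meeting Table 31's bilirubin route also meets the SAP cut. Laboratory omissions are thus confined to baselines below ULN with peaks no higher than 3 x ULN. Jaundice cases without a qualifying bilirubin value are omitted at any baseline.

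**Step 5: other planned displays.** SAP 8.4.2 also plans shifts from baseline by normal range and by CTCAE grade, and worsening by at least two grades. These treat analytes separately and do not join ALT/AST with bilirubin in one subject. SAP 8.1 plans a listing of all AESIs, which gives no incidence by arm. The renal screen in the same section does use multiples of baseline, so the liver screen's lack of a baseline term is not a convention of that section.

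**The case against.** The strongest reply is that the SAP follows the protocol's other wording. Table 29 uses the same numerical cuts as SAP 8.4.2, so the protocol is not uniform and Table 31 cannot be treated as its only description of DILI. That stands, and it is why the passages need reconciling. It does not justify the SAP count. Table 29 is a management table that requires the event to be drug-related and otherwise unexplained, and the SAP rows carry neither qualifier. The AESI that SAP 8.3 sets out to summarize is the one in Table 31.

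A second reply is that the SAP calls these screening criteria, and a screen may be broad. That is fair for the rows themselves, but SAP 8.3 makes them the whole DILI analysis and no definition-based table follows.

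Three stronger readings are tempting and are not supported:

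- A reader might infer that subjects with entirely stable liver tests will be counted as DILI. Step 3 shows otherwise: only the ALT/AST component can be pre-existing.
- A reader might infer that DILI cases will be lost. Protocol 8.3 requires AESI reports within 24 hours, Appendix K puts potential DILI in the clinical database, and SAP 8.1 lists all AESIs. What is missing is a by-arm tabulation.
- A reader might infer that many subjects enter above 3 x ULN, or that the bilirubin rises will usually reflect progression. The documents give no figure for either.

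**Conclusion.** The definitions conflict, and following the SAP as written gives a by-arm DILI count that does not match the protocol's AESI. The mismatch runs in both directions within the limits in Steps 2 to 4. Its frequency is unknown without a baseline ALT/AST distribution. The finding that bilirubin must rise rests on the assumed bilirubin ULN of 1.0 to 1.3 mg/dL; the rest follows from the stated thresholds. Safety summaries are descriptive, with no formal comparison planned between the experimental and control arms (SAP 8), and no primary or secondary efficacy endpoint is affected. It should still be corrected before reporting, because hepatic safety is a leading question in this population.

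**What to change.** In SAP 8.4.2, add a by-arm table of DILI AESIs on the Table 31 definition. Derive the bilirubin route from laboratory data; Protocol Table 2 already includes conjugated and unconjugated fractions. Derive the jaundice route from reported AE and AESI records using prespecified terms, since jaundice is not a laboratory variable and physical examination findings stay in source documents (Protocol 16.4).

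Keep the ULN-based Hy's Law rows as a screen, split by baseline ALT/AST at or below 3 x ULN and above 3 x ULN. Protocol Tables 28 and 29 already use that boundary.

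State in the SAP how the wording in Protocol Table 29, Protocol Table 31 and SAP 8.4.2 is reconciled for reporting. This concerns the analysis definition only; no clinical management rule is proposed.

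The cost is a small amount of extra programming, including the jaundice-term derivation. No new data collection is needed.
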